4.3. Exploratory Objectives

Exploratory Objectives	Exploratory Endpoints

 • To assess whether 80 mg ixekizumab every 2 weeks (Q2W) is superior to placebo at Week 12 in the treatment of genital psoriasis patients with baseline body surface area (BSA) $\geq 10\%$ as measured by overall Psoriasis Area and Severity Index (PASI) 	
 • Mean change from baseline in overall PASI at Week 12

 • To assess whether 80 mg ixekizumab Q2W is superior to placebo at Week 12 in genital psoriasis patients with baseline BSA $\geq 10\%$ as measured by overall PASI 75/90/100 	
 • The proportion of patients achieving overall PASI 75/90/100 at Week 12

 • To assess whether 80 mg ixekizumab Q2W is superior to placebo at Week 12 in patients with moderate-to-severe genital psoriasis as measured by: 
 ○ static Physician Global Assessment (sPGA) of Genitalia (0) ○ overall sPGA (0) 	
 • The proportion of patients achieving 
 ○ sPGA of Genitalia (0) at Week 12 ○ overall sPGA (0) at Week 12

 • To explore whether there is any impact of Fitzpatrick Skin Type on improvement measured by sPGA of Genitalia (0,1) response at Week 12 	
 • Association between Fitzpatrick Skin Type (reported at baseline) and sPGA of Genitalia (0,1) response at Week 12

 • To assess whether 80 mg ixekizumab Q2W is superior to placebo at Week 12 in the treatment of patients with moderate to severe genital psoriasis as measured by: 
 ○ GPSIS, Impact of Sexual Activity on Genital Psoriasis Symptoms Subscale for patients who reported as being sexually active at baseline (score of “0” on GPSIS Question 1) ○ Sexual Frequency Questionnaire (SFQ) item 1 ○ Comprehensive Assessment of the Psoriasis Patient (CAPP) Genital sub-index ○ Touch Avoidance NRS ○ Short Form 36 Question Health Survey (SF-36) individual domain scores 	
 • To assess whether 80 mg ixekizumab Q2W is superior to placebo at Week 12 in the treatment of patients with moderate to severe genital psoriasis as measured by: 
 ○ The proportion of patients whose degree of worsening is very low or none at all, or low, GPSIS Impact of Sexual Activity on Genital Psoriasis Symptoms Subscale score of 1 or 2, at Week 12. This will be calculated for patients who reported a score of “0” on GPSIS Question 1 at baseline and had a baseline score of at least 3 ○ The proportion of patients at each level of SFQ item 1 ○ Mean change from baseline in the total CAPP Genital sub-index score ○ Mean change from baseline in the Touch Avoidance NRS ○ The proportion of patients with at least a 5 point improvement from baseline in individual domain scores

Exploratory Objectives	Exploratory Endpoints

 To explore the impact of ixekizumab versus placebo at Week 12 on the change in presence of fissure, ulcer, and/or erosion in the genital area and its association with measures of disease severity and quality of life 	
 The proportion of patients with presence of genital fissure, ulcer, and/or erosion and the association of presence with measures of sPGA of Genitalia (0,1) response and quality of life (SF-36 mental component summary [MCS], Dermatology Life Quality Index [DLQI], GPSIS Subscales, and SFQ items) in the subgroup of patients with fissure, ulcer, and/or erosion

 To explore the impact of ixekizumab versus placebo at Week 12 on the change in presence of psoriasis in perianal/gluteal cleft area (as indicated by the investigator in the case report form) and its association with measures of quality of life 	
 The proportion of patients with presence of perianal/gluteal cleft psoriasis and the association of presence with measures of quality of life (SF-36 MCS, DLQI, GPSIS Subscales, and SFQ items) in the subgroup of patients with psoriasis located in perianal area and/or gluteal cleft area

 To explore the impact of ixekizumab versus placebo at Week 12 on the change in presence of psoriasis on the face and its association with measures of quality of life 	
 The proportion of patients with presence of facial psoriasis and the association of presence with measures of quality of life (SF-36 MCS, DLQI, and SFQ items) in the subgroup of patients with psoriasis located on the face

 To explore long-term impact of ixekizumab on symptoms and quality of life through Week 52 	
 The change over time through Week 52 in DLQI, SF-36 MCS, GPSS items, GPSIS Subscales, and SFQ items

 To assess the psychometric properties (including reliability, validity, and responsiveness) of the GPSS, GPSIS, SFQ, and sPGA of Genitalia 	
 Test-retest reliability, construct validity, and responsiveness will be assessed by Intra-class Correlation Coefficients (ICCs), Pearson correlation/Spearman rank-based correlation coefficient, and correlations of calculated changes in scores, respectively, or as deemed appropriate

 To measure ixekizumab exposure and assess the relationship between exposure and efficacy, and exposure and immunogenicity 	
 Serum trough concentrations of ixekizumab Model parameters for the exposure-response relationship between ixekizumab serum trough concentrations and efficacy endpoints Ixekizumab serum trough concentrations associated with ADA titer subgroups

 To explore biomarkers that are predictive of response to ixekizumab treatment that may be contained in DNA, RNA, serum, or plasma samples 	
 Association between biomarker and ixekizumab response

[figure not shown]
5. Study Design

5.1. Overview of Study Design

Study I1F-MC-RHBQ (RHBQ) is a Phase 3, multicenter, randomized, double-blind, placebo-controlled, parallel-group, outpatient study examining the efficacy and safety of ixekizumab as compared to placebo in patients with moderate-to-severe genital psoriasis. The study consists of 4 periods:

- **Period 1: Screening Period** (Visit 1 and Visit 1A) will assess patient eligibility and start e-diary data collection, occurring approximately 7 to 30 days prior to Period 2 (baseline; Week 0; Visit 2).
- **Period 2: Blinded Treatment Period** will occur from Week 0 (Visit 2) up to Week 12 (Visit 7). Patients will be randomized to ixekizumab or placebo in a 1:1 ratio. Two injections of ixekizumab 80 mg subcutaneous (SC) (total dose of 160 mg) or 2 injections of placebo SC, respectively, will be given at Week 0 (Visit 2). From Week 2 through Week 10 patients will receive ixekizumab 80 mg every 2 weeks (Q2W) SC or placebo Q2W SC.
- **Period 3: Open-Label Treatment Period** will occur from Week 12 (Visit 7) up to Week 52 (Visit 12). At Week 12 (Visit 7) 1 injection of ixekizumab 80 mg SC and 1 injection of placebo SC (total dose of ixekizumab 80 mg) will be given to patients who were randomized to ixekizumab in Period 2; and 2 injections of ixekizumab 80 mg SC (total dose of ixekizumab 160 mg) will be given to patients who were randomized to placebo in Period 2. During the remainder of Period 3, patients will receive ixekizumab 80 mg every 4 weeks (Q4W) dosing with an option to step-up to Q2W dosing starting at Week 24 through Week 40 (at Visit 9 [Week 24], Visit 10 [Week 28], or Visit 11 [Week 40]). This Open-label Treatment Period will allow evaluation of long-term efficacy and safety of ixekizumab through 1 year (52 weeks).
- **Period 4: Post-Treatment Follow-up** (Visit 801 through Visit 803) is for safety monitoring after treatment discontinuation for any patient receiving at least 1 dose of investigational product. Once patients complete the study treatment or discontinue study treatment early, patients will complete the Post-Treatment Follow-up (Period 4). For patients who have entered Period 4, psoriasis therapy is allowed, as determined appropriate by the investigator. This period occurs from the last treatment period visit or early termination visit (ETV) up to a minimum of 12 weeks following that visit.

Figure RHBQ.5.1 illustrates the study design.

Abbreviations: inj = injection; LV = date of last visit; LY = LY2439821 (ixekizumab); n = number of patients; pt = patient; PBO = placebo; Q2W = every 2 weeks; Q4W = every 4 weeks; SC = subcutaneous; V = visit; W = study week.

- ^a Patients who discontinue the study for any reason and who have received at least 1 dose of investigational product will continue to Early Termination Visit before entering the Post-Treatment Follow-Up Period.
- ^b All patients who increase dosing from 80 mg Q4W to 80 mg Q2W will remain on Q2W until completion of the study (W52 or early discontinuation) (Section 6.1).

Figure RHBQ.5.1. Illustration of study design for Clinical Protocol I1F-MC-RHBQ.

5.2. Method of Assignment to Treatment

Patients who meet all criteria for enrollment will be randomized to blinded treatment at Visit 2 (Week 0) in a 1:1 ratio to ixekizumab 80 mg Q2W or placebo. Assignment to treatment groups will be determined by a computer-generated random sequence using an interactive web-response system (IWRS). The IWRS will be used to assign double-blind investigational product to each patient. Site personnel will confirm that they have located the correct assigned investigational product package by entering a confirmation number found on the package into the IWRS.

To achieve between-group comparability for body surface area (BSA), the randomization will be stratified by BSA (1% to <10% versus $\geq 10\%$).

5.3. Determination of Sample Size

The total sample size for the study will be approximately 146 patients randomized at 1:1 ratio in the Blinded Treatment Period to ixekizumab Q2W and placebo (73 patients per treatment group).

No prior static Physician's Global Assessment (sPGA) of Genitalia (primary outcome measure) data was available at the time of planning this study to guide sample size and power calculations because no biologic drug has been evaluated in a well-controlled clinical trial to date in patients with genital psoriasis. Therefore, based on the relevance and impact of sexual impairment in genital psoriasis, data from the assessment of the Dermatology Life Quality Index (DLQI) Item 9 (How much has your skin caused any sexual difficulties?) outcomes in the ixekizumab Phase 2 and Phase 3 studies were used to calculate the sample size. Sample size was calculated assuming sexual impairment rates of 2% and 20% in the ixekizumab Q2W and placebo treatment groups, respectively. With these assumed rates, a sample size of 146 (73 per treatment group) is likely to achieve 94% power, based on a 2-sided Fisher's exact test at 0.05 level of significance.

6. A Priori Statistical Methods

6.1. General Considerations

Statistical analysis of this study will be the responsibility of Eli Lilly and Company (hereafter Lilly). The statistical analyses will be performed using SAS® Version 9.2 or higher.

Change from baseline at a particular visit will be calculated as the value at that visit minus the baseline value.

The means and medians will be reported to 1 more decimal place than the raw data recorded in the database. The standard deviation (SD) will be reported to 2 more decimal places than the raw data recorded in the database. In general, the maximum number of decimal places reported shall be 4 for any summary statistic.

Percentages will be presented to 1 decimal place. Percentages will not be presented for zero counts.

For outcome measures that are not collected at each post-baseline visit, data may exist at visits where the outcome measure was not scheduled to be collected, due to ETVs. In these situations, data from the ETVs that do not correspond to the planned collection schedule will be excluded from any mixed-effects models for repeated measures (MMRM) analysis. However, the data will still be used in other analyses, including shift analyses and other categorical analyses.

General Considerations for Analyses during Blinded Treatment Period (Period 2)

Comparisons of ixekizumab Q2W dosing versus placebo will be performed for all outcome variables in Period 2.

All confidence intervals (CIs) and statistical tests will be 2-sided unless otherwise specified. p-values which are greater than or equal to 0.001, and less than or equal to 0.999, will be presented to three decimal places. All other p-values which are less than 0.001 will be presented as <0.001, while p-values greater than 0.999 will be presented as >0.999. Confidence intervals will be presented to one more decimal place than the raw data.

General Considerations for Analyses during Open-label Treatment Period (Period 3)

Only summary statistics will be presented for the treatment groups:

- Ixekizumab 80 mg, every 2 weeks/every 4 weeks (IXE80Q2W/IXE80Q4W): Patients who received ixekizumab Q2W in the Blinded Treatment Period and ixekizumab Q4W in the Open-label Treatment Period (including those who stepped up to ixekizumab Q2W).
- Placebo/ixekizumab 80 mg, every 4 weeks (PBO/IXE80Q4W): Patients who received placebo in the Blinded Treatment Period and ixekizumab Q4W in the Open-label Treatment Period (including those who stepped up to ixekizumab Q2W).
- Overall: Unless otherwise specified, no comparisons between IXE80Q2W/IXE80Q4W and PBO/IXE80Q4W will be performed for any outcome variable in Period 3.

Data from patients who step up to ixekizumab Q2W dosing will be included in the efficacy summaries using the Open-label Treatment Population and the treatment groups defined above. The tables, figures, and listings will include footnotes indicating that patients were allowed to increase to Q2W dosing during the Open-label Treatment Period.

The number of patients who step up to Q2W dosing in Period 3 will be summarized by visit and overall using the treatment groups defined above. Patients who step up to Q2W dosing will be flagged in some efficacy and safety listings as deemed appropriate. A separate efficacy listing of sPGA of Genitalia and modified Genital Psoriasis Area and Severity Index (mGPASI) will be provided for patients who step up to Q2W dosing indicating the visits at which the patients started Q2W dosing.

6.1.1. Analysis Populations

Intent-to-treat Population: The Intent-to-treat (ITT) Population consists of all randomized patients. Even if the patients are not administered the assigned treatment, do not receive the correct treatment, or otherwise do not follow the protocol, they will be analyzed according to the treatment group to which they were assigned. Unless otherwise specified, all efficacy and health outcomes analyses during the Blinded Treatment Period will be conducted on the ITT Population.

Safety Population: The Safety Population is defined as all randomized patients who received at least 1 dose of study treatment. Patients will be analyzed according to the treatment group to which they were assigned. Unless otherwise specified, all safety analyses during the Blinded Treatment Period will be conducted on the Safety Population.

Open-label Treatment Population: The Open-label Treatment Population consists of all randomized patients who received at least 1 dose of study treatment during Period 3 and have entered the Open-label Treatment Period. Patients will be analyzed according to the treatment group to which they were assigned in Period 2, unless otherwise specified. All analyses for Period 3 (Open-label Treatment Period) will be conducted on this analysis population.

Post-Treatment Follow-Up Population: The Post-Treatment Follow-up Population consists of all randomized patients who received at least 1 dose of study treatment during Period 2 and have entered the Post-Treatment Follow-up Period. Patient data will be summarized according to the treatment group that the patient is assigned prior to entering the Post-Treatment Follow-up Period. Safety analyses for Period 4 (Post-Treatment Follow-up Period) will be conducted on this analysis population.

Table RHBQ.6.1. Treatment Group and Comparisons for Each Study Period and Analysis Population

Study Period	Analysis Population	Treatment Group	Abbreviation	Comparison
Blinded Treatment Period (Period 2)	Intent-to-treat Population; Safety Population	Ixekizumab 80 mg Q2W	IXE80Q2W	IXE80Q2W vs. PBO
		Placebo	PBO	
Open-label Treatment Period (Period 3)	Open-label Treatment Population	Ixekizumab 80 mg Q2W / Ixekizumab 80 mg Q4W	IXE80Q2W/IXE80Q4W	No comparison
		Placebo / Ixekizumab 80 mg Q4W	PBO/IXE80Q4W	
Post-Treatment Follow-up Period (Period 4) ^a	Post-Treatment Follow-up Population	Placebo	PBO	No comparison
		Ixekizumab 80 mg Q2W	IXE80Q2W	
		Ixekizumab 80 mg Q4W	IXE80Q4W	

Abbreviations: IXE = ixekizumab; PBO = placebo; Q2W = every 2 weeks; Q4W = every 4 weeks; vs. = versus.

^a Refers to the treatment group that the patient is assigned prior to entering the Post-Treatment Follow-up Period.

Note: The treatment before the slash indicates the treatment assigned in the Blinded Treatment Period and the treatment after the slash indicates the treatment assigned in the Open-label Treatment Period.

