
 • Time course of response to treatment as measured by sPGA of Genitalia (0,1) 	
 • The proportion of patients who achieve sPGA of Genitalia (0,1) over time through Week 52

 • Time course of response to treatment as measured by mGPASI 	
 • Mean change in mGPASI over time through Week 52

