6.3. Handling of Dropouts or Missing Data

The methods for imputation of missing data to be used in this study are in accordance with the precedent set in other Phase 3 psoriasis trials (Leonardi et al. 2008; Papp et al. 2008) and ixekizumab Phase 3 pivotal studies (I1F-MC-RHAZ [RHAZ], I1F-MC-RHBA [RHBA], and I1F-MC-RHBC [RHBC]).

The methods for imputation of missing data to be used in this study are described below.

6.3.1. *Non-responder Imputation (NRI)*

Analysis of categorical efficacy and health outcome variables will be based on treatment success / failure. This approach yields results numerically identical to non-responder imputation (NRI), but it is interpreted differently. Patients will be considered treatment failures if they do not meet the clinical response criteria or have missing clinical response data at a particular time point of analysis.

With NRI, as the acronym implies, there is explicit imputation of missing sPGA of Genitalia (0,1) outcomes. With treatment success / failure, discontinuation of study medication is considered a treatment failure because if patients cannot adhere to the medication they will not have sustained benefit from it. Therefore, every patient will have an observation for treatment success / failure and there will be no missing data for this estimand and hence inferences will not depend on missing data assumptions. These attributes also apply to other endpoints involving use of NRI. Randomized patients without at least 1 post-baseline observation will also be defined as non-responders for the NRI analysis.

6.3.2. *Modified Baseline Observation Carried Forward (mBOCF)*

An mBOCF analysis will be performed on the continuous efficacy and health outcome variables defined as “major” or “other” secondary outcome variables in Section 4.3. For patients discontinuing investigational product due to an adverse event (AE), including death, the baseline observation will be carried forward to the corresponding primary endpoint for evaluation. For patients discontinuing investigational product for any other reason, the last non-missing post-

baseline observation before discontinuation will be carried forward to the corresponding time point of evaluation. Randomized patients without at least 1 post-baseline observation will not be included for evaluation with the exception of patients discontinuing study treatment due to an AE (including death).

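### After Week 12 SAP 6.1.1 moves the genital response time course from all randomized patients to those dosed in Period 3, so rates through Week 52 can carry an upward component; Table RHBQ.6.5 does not settle which population applies

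*SAP*

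**What the plan says.** SAP 4.2 lists among the other secondary endpoints "The proportion of patients who achieve sPGA of Genitalia (0,1) over time through Week 52", and states a companion endpoint for mean change in mGPASI over the same span.

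SAP 6.1.1 fixes the populations by period. "The Intent-to-treat (ITT) Population consists of all randomized patients", and unless otherwise specified "all efficacy and health outcomes analyses during the Blinded Treatment Period will be conducted on the ITT Population". For the next period, "The Open-label Treatment Population consists of all randomized patients who received at least 1 dose of study treatment during Period 3", and "All analyses for Period 3 (Open-label Treatment Period) will be conducted on this analysis population". That last sentence has no exception clause. Table RHBQ.6.1 and protocol 9.3 agree with it. SAP 6.1 adds that data from patients who step up to Q2W "will be included in the efficacy summaries using the Open-label Treatment Population and the treatment groups defined above".

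On missing binary data, SAP 6.3.1 says "Patients will be considered treatment failures if they do not meet the clinical response criteria or have missing clinical response data". SAP 6.11 treats anyone who stops treatment before Week 12 as a failure. Under protocol 7.1 such patients go to the early termination visit and then to Period 4, where the Schedule of Activities has no sPGA of Genitalia.

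Three other places point elsewhere or leave the matter open:
- Table RHBQ.6.5 gives ITT as the only population for sPGA of Genitalia (0,1), at Week 12 and at all other visits after baseline.
- Footnote b of that table counts open-label visits among the post-baseline visits for the diary measures.
- SAP 6.16.2.2 uses evaluable ITT patients for the antibody-by-efficacy analyses in both periods.

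**The concern.** Under 6.1.1, a patient who drops out in Period 2 is in the denominator as a failure up to Week 12 and absent from Week 16 on. Removing counted failures raises the response rate even if no patient's skin changes. The endpoint is worded as one course through Week 52, so readers will compare the Week 12 figure with later ones. Part of any apparent gain or maintenance after the move from Q2W to Q4W dosing could then come from the change of denominator. No passage requires Week 12 to be shown again on the open-label population.

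The conflict with Table RHBQ.6.5 matters separately. A programmer could produce the Week 52 rate on either population and point to SAP text in support, and the two figures would differ.

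**Working it through.** **Inputs.** The documents give no expected dropout rate and no expected sPGA of Genitalia response rate, so both are assumed. The plan has no figure of its own on this point. The only number taken from it is 73 patients per arm (SAP 5.3). The 94% power stated there reproduces at 94.7% by exact enumeration for Fisher's test, but does not bear on this point.

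**Formula.** Let N be randomized to the arm, D of them never dosed in Period 3 and all failures at Week 12, and X responders at Week 12. Suppose nobody changes status by Week 16.

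- ITT with NRI at Week 12: X/N = R
- Open-label Treatment Population at Week 16: X/(N-D)
- Artificial step: X/(N-D) - X/N = R*d/(1-d), with d = D/N

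**Size (points), for assumed R and d**

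| d | R = 60% | R = 75% |
|---|---|---|
| 0% | 0 | 0 |
| 5% | +3.2 | +3.9 |
| 10% | +6.7 | +8.3 |
| 15% | +10.6 | +13.2 |

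For example, 0.60 x 0.05/0.95 = 3.2 points and 0.75 x 0.15/0.85 = 13.2 points.

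**Whole-patient example.** Take N = 73, D = 7 and X = 44. Week 12 on ITT is 44/73 = 60.3%. Week 16 on the open-label population is 44/66 = 66.7%, a rise of 6.4 points with no patient changed. On one denominator there is no step: 60.3% at both visits on ITT with NRI, or 66.7% at both on the open-label population.

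**What can hide or reverse the step**
- Real loss of response: if 5 of the 44 responders are lost by Week 16, the open-label rate is 39/66 = 59.1%, below 60.3%. ITT with NRI would show 39/73 = 53.4%, so the open-label figure is still 5.7 points higher.
- Week 12 responders who take no Period 3 dose: if 4 of the 7 undosed patients were responders, the step is 40/66 - 44/73 = +0.3 points; if 5 were, it is 39/66 - 44/73 = -1.2 points.

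**Later visits.** Undosed patients normally have no sPGA of Genitalia from Week 16 on, so ITT with NRI counts them as failures at each visit. With NRI on both populations, the open-label rate at any Period 3 visit, including Week 52, is the ITT rate divided by (1-d).

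**Placebo-randomized arm.** With an assumed 4 of 73 responding at Week 12 (5.5%), the step is +0.3 points at D = 4 and +1.0 at D = 11. A Week 16 rise there is in any case confounded with starting ixekizumab at Week 12.

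**The case against.** The strongest reply is that the SAP never says the two periods are joined. Table RHBQ.6.1 gives each period its own population and group labels, and for Period 3 SAP 6.1 says "Only summary statistics will be presented for the treatment groups". Two labelled segments, one per population, would satisfy the endpoint wording. A reader might infer that the SAP prescribes a single spliced curve; no passage says so. What stands is that the endpoint invites the comparison across Week 12 and nothing in the plan supplies a like-for-like Week 12 value.

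A second reply is that the conflict may be only apparent. The table's methods for this variable include logistic regression and Fisher's test, while SAP 6.1 plans no Period 3 comparisons unless otherwise specified, so the table may be meant for Period 2 only. If instead its ITT entry extends to Period 3, the denominator does not change and the artefact disappears. Both readings are possible. Footnote b and SAP 6.16.2.2 favour the wider one, and the text does not choose. This makes the size conditional on 6.1.1 governing and leaves the need for clarification intact.

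A third reply is that conditioning on starting open-label treatment is openly defined and is a legitimate choice. That is fair for a segment read alone. It does not cover comparison with an ITT value at Week 12.

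**Conclusion.** The point holds in conditional form. If SAP 6.1.1 governs, the Week 12 to Week 16 change and the later response rates in the ixekizumab-randomized arm contain an upward component. For the Week 12 to Week 16 change it is about R*d/(1-d), roughly +3 to +13 points for R of 60% to 75% and d of 5% to 15%. It rests on assumed rates and on every undosed patient being a Week 12 failure.

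Three stronger readings are not supported:
- That response must rise at Week 16. The component is zero without dropout, and lost response or undosed Week 12 responders can mask or reverse the step.
- That mean change in mGPASI is inflated by the same amount. It is analysed by MMRM and by ANCOVA with mBOCF, so no NRI failures leave the denominator. Only the patient mix changes, and the documents give neither direction nor size.
- That the trial's claims are at risk. Period 3 is descriptive, and the whole testing sequence in SAP 6.4 is at Week 12.

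The change should be made because it is cheap and removes an ambiguity in a named secondary endpoint.

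**What to change.** 1. Reconcile SAP 6.1.1 with Table RHBQ.6.5 by naming, for each through-Week-52 endpoint, the population and missing-data rule that apply after Week 12.
2. Summarise sPGA of Genitalia (0,1) for the ixekizumab-randomized arm on ITT with NRI at every visit through Week 52.
3. Also present the Open-label Treatment Population series, with its Week 12 point recomputed on that same population.
4. For mean change in mGPASI, show Week 12 on the Open-label Treatment Population beside the Period 3 values, under a stated rule for continuous data. NRI cannot be used for a mean change.

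The cost is SAP wording and a few extra summaries. The Week 52 response rate on ITT will be slightly lower than on the open-label population. Data collection, sample size and the confirmatory tests do not change.
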